#### 9.1.4 Pooling

Placebo subjects will be pooled for summary TFLs for this study.

#### 9.1.5 Unscheduled Measurements

Unscheduled measurements will be included in the listings. In general, except for unscheduled measurements used for baseline, unscheduled measurements will be excluded from the descriptive statistics and statistical analysis by timepoint. For shift tables or tables that summarize worst outcome, unscheduled measurements (occurring after previous timepoint and up to and including each scheduled timepoint) will be included in summary statistics.

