11.3. Assessment of Safety

11.3.1. Safety Parameters

11.3.1.1. Vital Signs

Vital signs include measurements of heart rate, BP, and temperature. BP (systolic and diastolic), pulse rate, and temperature should be taken after the subject has rested in the supine position for at least 10 minutes. Respiratory rate is a required vital sign at Screening for eligibility and should be taken after the subject has rested in the supine position for at least 10 minutes. BP measurements must be obtained with an appropriate cuff size and with the subject's arm supported at the level of the heart. It is acceptable to obtain a pulse rate from the BP or ECG machine. Grade 2 or higher vitals will be repeated in 30 minutes if abnormal.

Pre-dose vital signs must be collected within 2 hours of the IV infusion. Post dose vital signs may be obtained within 10 minutes of the nominal time point. Any abnormality should be graded on a scale from 0 (none) to 3 (severe) using the modified 2014 DMID Adult Toxicity Grading Scale; [APPENDIX A](#)) and reported as an AE if appropriate as per Section [11.4.1.1](#). If the event is more severe than a Grade 3, severity criteria as described in Section [11.4.1.2](#) should be used to characterize the event.

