11.3.1.3. Physical Examination

A PE consisting of the head and neck, skin, chest (lungs and heart), abdomen (gastrointestinal tract, liver, spleen and kidneys), back, musculo-skeletal system, neurologic system should be conducted at screening and at discharge from the unit. Breast and genitourinary system do not require examination unless the potential subject indicates a complaint or comorbidity that could result in exclusion.

All subsequent PEs may be symptom driven based on the subject's interim medical history.

11.3.1.4. 12-Lead Electrocardiogram

A standard bedside 12-lead ECG machine that calculates heart rate and measures the PR, QRS, QT, RR, and QTc (QTcF) intervals will be utilized. Prior to obtaining an ECG, subjects must rest quietly in a supine position for at least 10 minutes.

Qualified site personnel should review the ECGs and automated findings from the Day 1 pre-dose and post dose ECGs prior to the next day's dosing or scheduled assessments for gross abnormalities and interval measurements of concern (absolute readings and for post dose ECGs,

change from baseline). For all ECGs, the clinical interpretation of the ECG should be recorded directly on a hard copy of the ECGs. Copies of the ECGs may be requested by the Sponsor.

Screening and baseline (Day 1 pre-dose) ECGs will be obtained in triplicate at 1- to 5-minute intervals, with baseline values calculated from an average of the three readings. The pre-dose ECG should be collected within \leq 2 hours of the first dose. Thereafter, single assessment ECG will be performed on Day 1 at 2 and 4 hours post dose, Day 2 at 24 hours post-dose and on Days 3 and 4 while the subject is in the CRU. An acceptable window is \pm 10 minutes from the nominal time point while the subject is in the CRU. An ECG will also be performed at the Day 21 follow-up visit. All ECGs should be obtained per the schedule of assessments in [Table 5](#).

An ECG should be repeated for a change from baseline in QTcF $>$ 30 ms.

An ECG will also be performed if a Grade 3 electrolyte abnormality (such as hyperkalemia) is detected to determine if there are any ECG-related changes and/or arrhythmias. ECGs will also be performed if a subject reports any AE symptoms that are indicative of cardiac signs or symptoms.

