12.3.1.3. Analysis of Safety Variables

AEs will be mapped to a Medical Dictionary for Regulatory Activities (MedDRA) preferred term (PT) and system organ classification (SOC). Any event reported on the subject's study record that occurs on or after the initiation of study drug is defined as treatment emergent. Additionally, it is assumed that an AE that is reported to have started on Day 1 of a given treatment period without an associated onset time may have occurred after the initiation of study drug. Hence, AEs occurring on Day 1 with no associated onset time will be assumed to be treatment emergent. The occurrence of TEAEs will be summarized by cohort and treatment assignment using MedDRA PTs, SOCs, and severity. Separate summaries of treatment-emergent SAEs and AEs considered to be related to study drug will be generated. All AEs will be listed for individual subjects showing both verbatim and preferred terms.

Descriptive summaries of vital signs, ECG parameters (12 lead and telemetry), ECHOs, and clinical laboratory results will be presented separately for each cohort by study visit and treatment assignment. Laboratory abnormalities will be graded according to the modified DMID criteria ([APPENDIX A](#)).

Any graded abnormality that occurs following the initiation of study drug and represents at least one grade increase from the baseline assessment is defined as treatment emergent. The number and percentage of subjects experiencing treatment-emergent graded toxicities will be summarized by treatment group. Laboratory toxicity shifts from baseline to post-baseline assessments will be summarized by treatment group.

PE results will be presented in listings. Changes in PE results that are AEs will be reported in AE tables.

Concomitant medications will be coded using the World Health Organization (WHO) Dictionary. These data will be summarized by cohort and treatment assignment.

Subjects receiving placebo will be pooled and reported together across cohorts.

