### 17.1.3 Laboratory Data

Clinical laboratory data will be presented using units from the study data tabulation model (SDTM) Controlled Terminology.

A descriptive statistics summary of continuous laboratory results and derived changes from baseline for cardiac markers, chemistry, coagulation, hematology, and urinalysis will be provided by cohort and scheduled timepoint.

Laboratory abnormalities outside of the normal laboratory reference ranges and associated grades (according to study specific DMID criteria specified in the 2014 DMID Adult Toxicity Grading Scale in Appendix 5) should be denoted where possible. For those analyte results that are out of the normal range and do not have an established DMID toxicity criteria, the severity grading will be provided by the PI. The number and percentage of subjects experiencing treatment-emergent graded toxicities will be summarized.

A shift table describing the change in continuous clinical laboratory values from baseline to follow-up (number and percentage of subjects) will also be provided. The following categories will be used: Normal, DMID Grade 1, DMID Grade 2, DMID Grade 3, DMID Grade 4.

All laboratory data will be listed by subject, including laboratory variables not listed in the protocol.

A separate listing of out-of-range values will also be provided. Normal ranges will be used directly from the clinical laboratory and will be included in the listings for reference. Flags for high and low values will be provided in the listings.

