#### **17.1.4 Vital Signs**

A descriptive statistics summary of vital signs and derived changes from baseline will be provided by cohort and treatment, and scheduled timepoint. Baseline is defined as measurement prior to initiation of treatment on Day 1 of each treatment period, where available.

All vital signs data will be listed by subject.

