#### **17.1.5 Electrocardiograms**

A descriptive statistics summary of 12-lead ECG parameters and derived changes from baseline will be provided by cohort and treatment, and scheduled timepoint. Where triplicate ECGs are taken, the average parameter values of the triplicates will be reported. Baseline is defined as the average of triplicate measurements prior to initiation of treatment on Day 1 of each treatment period, where available.

A summary table for QTcF categories ( $\leq 450$  msec,  $>450$  to  $\leq 480$  msec,  $>480$  to  $\leq 500$  msec, and  $> 500$  msec) by cohort and treatment, and timepoint will be presented. The table will also summarize the number and percentage of subjects with change from baseline for categories of  $\leq 30$  msec, 30 msec to  $\leq 60$  msec, and  $> 60$  msec.

All 12-lead ECG parameters, physician's conclusions, and corresponding abnormalities will be listed by subject.

Descriptive statistics will be provided to summarize mean ECG parameters (observed and changes from baseline) by treatment, visit, and scheduled time.

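### No ECG or vital-sign table in the SAP is specified to take unscheduled readings, so repeat and symptom-triggered values can be missing from those summaries

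*SAP*

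**What the plan says.** SAP 9.1.5 puts unscheduled measurements in the listings. Then, in general and apart from values used as baseline, "unscheduled measurements will be excluded from the descriptive statistics and statistical analysis by timepoint". The same paragraph makes an exception: "For shift tables or tables that summarize worst outcome, unscheduled measurements" are included in the summary statistics.

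The ECG and vital-sign outputs are organised by time:

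- SAP 17.1.4: "A descriptive statistics summary of vital signs and derived changes from baseline will be provided by cohort and treatment, and scheduled timepoint".
- SAP 17.1.5: the continuous ECG summary is by scheduled timepoint, and the absolute QTcF categories "by cohort and treatment, and timepoint will be presented". The next sentence adds counts of subjects in categories of QTcF change, without saying whether these are by timepoint or at the worst value.
- SAP Appendix 3 lists Table 14.3.6 (vital signs), Table 14.3.7.1 (ECG results) and Table 14.3.7.2 (QTcF categories). It names no shift, graded or worst-value table for either domain.

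The only shift table is for laboratory data. SAP 17.1.3 describes it as "A shift table describing the change in continuous clinical laboratory values from baseline to follow-up". Protocol 12.3.1.3 says: "Laboratory toxicity shifts from baseline to post-baseline assessments will be summarized by treatment group".

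The protocol creates off-schedule readings deliberately. Section 11.3.1.4 asks for a repeat ECG when QTcF rises more than 30 ms from baseline, an ECG with a Grade 3 electrolyte abnormality, and one for symptoms: "ECGs will also be performed if a subject reports any AE symptoms that are indicative of cardiac signs or symptoms". Section 11.3.1.1 states: "Grade 2 or higher vitals will be repeated in 30 minutes if abnormal".

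**The concern.** ECGs and vital signs are named primary endpoints. SAP 9.1.5 has a sensible rule for letting unscheduled values into worst-outcome tables, but no ECG or vital-sign output is described as such a table, so the rule has nothing to act on there. The readings left out are those taken because something had already looked abnormal or a subject had symptoms.

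At stake is the per-subject answer a reader wants from a Phase 1 report: how many subjects on each dose ever exceeded 480 or 500 ms, ever rose more than 60 ms, or ever reached a given blood pressure grade. By-timepoint rows do not give that count even for scheduled readings, and they omit off-schedule ones altogether.

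The laboratory wording is a smaller matter. In SAP Appendix 2, follow-up is the name of the Day 21 visit, so the shift table could be programmed as baseline to Day 21 only. The protocol's phrase is broader, and SAP 7.1 declares no changes from the protocol.

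**Working it through.** The plan states no power or event figure on this point, so there is nothing to reproduce. The check sets the SAP 9.1.5 rule against each planned output.

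**Step 1. Which outputs admit unscheduled readings?**

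| Output | Organisation in the SAP text | Unscheduled readings in? |
|---|---|---|
| Table 14.3.6, vital signs | scheduled timepoint | No |
| Table 14.3.7.1, ECG | scheduled timepoint | No |
| Table 14.3.7.2, absolute QTcF | timepoint | No |
| Table 14.3.7.2, QTcF change | not stated | Cannot be determined |
| Table 14.3.5.2, laboratory shifts | shift table | Yes |
| Listings 16.2.9 and 16.2.10 | by subject | Yes |

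**Step 2. Effect on a count.** Inputs: 6 galidesivir subjects per cohort and 4 cohorts (Protocol 7.2), so 4 × 6 = 24 active subjects. Assumed for illustration: one subject has every scheduled QTcF at or below 480 ms and one symptom-triggered reading of 485 ms.

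- By-timepoint rows, above 480 ms: 0/6 in every row.
- Worst-post-baseline row including unscheduled readings: 1/6 = 16.7% of the cohort's active arm, or 1/24 = 4.2% of all active subjects.

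**Step 3. Where an off-schedule ECG could matter.** The infusion ends at 1 h. The first scheduled post-dose ECG is at 2 h, with a window of 10 minutes either side (Protocol Table 5, footnote d). A 12-lead QTcF at the end of infusion can therefore come only from an off-schedule recording. Protocol 11.3.1.5 allows a telemetry finding to trigger an ECG, and SAP 17.1.6 plans only a listing for telemetry itself.

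**Step 4. What is not lost.** Scheduled post-dose blood pressure times in the first 24 hours are 1, 2, 4, 8 and 24 h (Table 5, footnote g), giving 5 × 4 / 2 = 10 pairs. Protocol 7.6.2 requires two readings at least 2 h apart for confirmation. At nominal times 9 of the 10 pairs qualify; only 1 h with 2 h does not. The 2 h and 4 h pair is exactly 2 h apart, so the 10-minute window in 11.3.1.1 could bring it below 2 h. Scheduled readings alone can thus confirm the blood pressure criterion, and they stay in Table 14.3.6. A scheduled QTcF above 480 ms likewise stays in Table 14.3.7.2; only its repeat is dropped.

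The loss is therefore limited to repeats, other off-schedule readings, whether an outlier was confirmed, and any per-subject count of ever having crossed a threshold.

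**The case against.** The strongest reply is that nothing important disappears. Adverse events are themselves a primary endpoint. Abnormal vital signs are graded and reported as adverse events where appropriate (Protocol 11.3.1.1), and clinically relevant abnormal diagnostic results are adverse events (11.4.1.1). They then appear in the treatment-emergent tables, including the one by severity. Every value is listed, and with six active subjects per cohort a listing is readable.

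This stands against a reading that a reader might infer: that off-schedule values never reach any primary-endpoint summary. The documents do not support that. It does not close the gap, because entry to the adverse event tables depends on judgement. In the earlier intramuscular study (Protocol 4.3.1.3), Grade 2 or 3 potassium elevations, judged likely pseudohyperkalemia, occurred with no adverse events at those times. Listings give no count by dose.

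Three other inferences also fail:

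- **That every reading behind the stopping rules is unscheduled.** Step 4 shows otherwise.
- **That stopping decisions are impaired.** The dose escalation committee receives per-cohort listings of vital signs and QT findings (Protocol 11.5.2), and the safety monitoring committee reviews all available safety data when halting criteria are met (11.5.3).
- **That laboratory changes resolved by Day 21 go unsummarised.** Table 14.3.5.3 counts treatment-emergent graded toxicities, which Protocol 12.3.1.3 defines as any post-dose rise of at least one grade. SAP 9.1.5 also refers to each scheduled timepoint when it describes shift tables, which points away from a Day 21-only reading. What remains is a wording mismatch.

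Finally, the shells are approved as part of the SAP (9.5) but kept in a separate document. They may already contain a worst-value row, and the change-category sentence leaves room for one.

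**Conclusion.** The point holds as a reporting gap. As written, the SAP text and output list specify no shift, graded or worst-value output for ECGs or vital signs, so the 9.1.5 exception has no such table to work through. Off-schedule ECGs and repeat vital signs can be absent from Tables 14.3.6, 14.3.7.1 and the absolute part of 14.3.7.2.

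Its size is a possible difference of one or more subjects in a small denominator: 0/6 against 1/6 in the illustration. The documents give no basis for estimating how often this would happen. The conclusion assumes that the shells add no worst-value row and that the general rule in 9.1.5 is applied without exception to these tables. Safety oversight during the study is unaffected. The improvement is worth making because it is cheap and concerns a primary endpoint.

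**What to change.** 1. **SAP 17.1.5 and Table 14.3.7.2.** Add a per-subject worst-post-baseline row for absolute QTcF and for change from baseline, using scheduled and unscheduled readings. State whether the existing change categories are by timepoint or at the worst value. Flag whether each outlier was confirmed on repeat.
2. **SAP 17.1.4 and Appendix 3.** Add a summary of worst post-baseline grade, on the Appendix 5 scale, for blood pressure and heart rate, again including unscheduled readings.
3. **SAP 17.1.3.** Replace the reference to follow-up with wording that matches Protocol 12.3.1.3, for example worst post-baseline grade.

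The cost is SAP wording and a few table rows from data already collected. The drawback is that worst-value counts include unconfirmed outliers: a scheduled outlier refuted by its repeat would still be selected. The confirmation flag in item 1 lets a reader see this for QTcF, and the by-timepoint tables should stay alongside.

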### 9.2 Analysis Data Definitions

#### 9.2.1 Baseline Definition

Unless otherwise stated, baseline for post dose evaluations is defined as the last observation recorded before the first study drug administration for each regimen as indicated in Appendix 2 (Schedule of Assessments). The last observation can be an unscheduled/repeated measurement. Baseline ECGs will

be calculated from an average of the triplicate readings prior to initiation of treatment on Day 1 of each treatment period.

### 9.2.2 Treatment/Subject Grouping

Throughout this SAP, study drug refers to: BCX4430 galidesivir for IV infusion.

Label	Grouping
Study Drugs	BCX4430 galidesivir for IV infusion
Treatment	
Cohort 1:
 
 
Regimen A: Galidesivir (Dose 5 mg/kg, Calculated Dose Range 250-500 mg, Concentration 1.0 mg/mL, Dose Volume 250-500 mL), or
 
Placebo (Dose Volume 250-500 mL)
 
 
Cohort 2:
 
 
Regimen B: Galidesivir (Dose 10 mg/kg, Calculated Dose Range 500-1000 mg, Concentration 1.0-2.0 mg/mL, Dose Volume 500 mL), or
 
Placebo (Dose Volume 500 mL)
 
 
Cohort 3:
 
 
Regimen C: Galidesivir (Dose 15 mg/kg, Calculated Dose Range 750-1500 mg, Concentration 1.5-3.0 mg/mL, Dose Volume 500 mL), or
 
Placebo (Dose Volume 500 mL)
 
 
Cohort 4:
 
 
Regimen D: Galidesivir (Dose 20 mg/kg, Calculated Dose Range 1000-2000 mg, Concentration 2.0-4.0 mg/mL, Dose Volume 500 mL), or
 
Placebo (Dose Volume 500 mL)
 

Dose Levels	
BCX4430: 5 mg/kg, Calculated Dose Range 250-500 mg
 
BCX4430: 10 mg/kg, Calculated Dose Range 500-1000 mg
 
BCX4430: 15 mg/kg, Calculated Dose Range 750-1500 mg
 
BCX4430: 20 mg/kg, Calculated Dose Range 1000-2000 mg
 
[Note: Treatment labels will use mg/kg]

### 9.2.3 Common Variable Derivations

Variable	Data Type	Definition/Calculation
Change from baseline	All	Post-dose observation minus baseline observation
Analysis study day (prior to dose)	All	Date of measurement minus dose date
Analysis study day (post dose)	All	Date of measurement minus dose date + 1
TEAE	AE	An AE is a treatment-emergent adverse event (TEAE) if the AE start date/time is greater than or equal to the first dose date/time

Abbreviations: AE = adverse event; TEAE = treatment-emergent adverse event.

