11.4. Adverse Events and Serious Adverse Events

AEs will be assessed and recorded from the time of signing the ICF through the appropriate follow-up period.

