11.4.1. Definition of Adverse Events

11.4.1.1. Adverse Event

An AE is any untoward medical occurrence in a clinical study subject. No causal relationship with the study drug/IMP or with the clinical study itself is implied. An AE may be an unfavorable and unintended sign, symptom, syndrome, or illness that develops or worsens during the clinical study. Clinically relevant abnormal results of diagnostic procedures including abnormal laboratory findings (eg, requiring unscheduled diagnostic procedures or treatment measures, or resulting in withdrawal from the study) are considered to be AEs. Abnormal laboratory findings that are not deemed clinically significant by the Investigator are not considered to be AEs.

This includes the following:

- AEs not previously observed in the subject that emerge during the protocol-specified AE reporting period (see Section 11.4).

- Findings from protocol-mandated interventions. This can include laboratory assessments performed during the clinical study. AEs should only be reported if the abnormalities are changes from baseline and are clinically significant as described above.
- Pre-existing medical conditions judged by the Investigator to have worsened in severity or frequency or changed in character during the protocol-specified AE reporting period.

An adverse reaction is defined in Article 2(n) of Directive 2001/20/EC as follows: all untoward and unintended responses to a study drug/IMP related to any dose administered. The definition also covers medication errors and uses outside what is foreseen in the protocol, including misuse and abuse of the product. The definition implies a reasonable possibility of a causal relationship between the event and the study drug/IMP. This means that there are facts (evidence) or arguments to suggest a causal relationship.

Surgical procedures should not be reported as AEs. The condition for which the surgery is required should be reported as the AE, if it occurs or is detected during the study period. Planned surgical measures permitted by the clinical study protocol and the conditions(s) leading to these measures are not AEs, if the condition(s) was (were) known before the start of study treatment. In the latter case the condition should be reported as medical history.

AEs are designated as “nonserious” or “serious.”

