Moderate: (Grade 2): Symptom results in mild to moderate limitation in activity; no or minimal intervention required. The AE produces some impairment of functioning, but it is not hazardous to health. It is uncomfortable or an embarrassment.

Severe: (Grade 3): Symptom results in significant limitation in activity; medical intervention may be required. The AE produces significant impairment of functioning or incapacitation.

Severity refers to the medical perspective of an event whereas seriousness reflects the outcome of the event (ie, hospitalization). Events of mild severity can lead to hospitalization and therefore be serious whereas severe events such as a headache may not meet seriousness criteria.

Changes in the severity of an AE should be documented to allow an assessment of the duration of the event at each level of intensity to be performed. AEs characterized as intermittent require documentation of onset and duration of each episode.

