### 17.1.1 Adverse Events

An AE is defined as any new untoward medical occurrence or worsening of a preexisting medical condition in a clinical investigation participant that does not necessarily have a causal relationship with treatment. TEAEs are those which occur during or after the administration of the first dose of study drug. All TEAE summaries will be presented alphabetically by system organ class, with preferred terms sorted in decreasing order of frequency within each system organ class based on MedDRA Version 21.1.

The following missing data will be imputed (for calculations only) as defined:

- Missing AE start and / or end times for the calculation of onset and duration will be assumed to be at 00:01 for a start time and 23:59 for end times
- Missing AE severity or relationship will be assumed to be severe or related, respectively
- Missing AE start times for the determination of treatment emergence will be assumed to occur after treatment unless partial date documents the AE as happening prior to treatment
- Missing AE start times for the determination of treatment assignment will be assumed to occur after treatment on the recorded date 1 minute after dosing
- Missing AE start date will be assumed to be after treatment for the determination of TEAE but will not be attributed to a specific study drug

A summary of the number and percentage of subjects reporting AEs, TEAEs, serious AEs (SAEs), and who discontinued study drug due to an AE will be provided by cohort and overall for the study.

A summary of the number and percentage of subjects reporting each TEAE will be provided by cohort and treatment, and overall. Counting will be done by subject, not by event; subjects will only be counted once within each system organ class or preferred term.

A summary of the number and percentage of subjects reporting each TEAE will be provided by relationship to treatment (BCX4430 formulation, as recorded on eCRF) and by cohort and treatment, and overall. Subjects with multiple events will be counted under the category of their most-related event within each system organ class or preferred term.

A summary of the number and percentage of subjects reporting each TEAE will be provided by severity (as recorded on eCRF) and by cohort and treatment, and overall within each cohort. Subjects with multiple events will be counted under the category of their most severe event within each system organ class or preferred term.

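### The TEAE rule uses AE start time alone, so an AE that is open at infusion, kept as one record and worsens after the dose would be left out of the detailed TEAE tables

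*SAP*

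**What the plan says.** Three places define treatment emergence for AEs.

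- SAP 9.2.3 gives the derivation to be programmed: "An AE is a treatment-emergent adverse event (TEAE) if the AE start date/time is greater than or equal to the first dose date/time".
- SAP 17.1.1 restates it in words: "TEAEs are those which occur during or after the administration of the first dose of study drug".
- Protocol 12.3.1.3 covers any event on the study record "that occurs on or after the initiation of study drug is defined as treatment emergent".

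None mentions an event that began before the dose and became worse after it. The rule for incomplete data also turns on onset: "Missing AE start times for the determination of treatment emergence will be assumed to occur after treatment unless partial date documents" an earlier event.

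Three other provisions bear on the point.

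- Collection window: "AEs will be assessed and recorded from the time of signing the ICF" (protocol 11.4). The schedule of assessments (protocol Table 5) has AE assessment on Day -1 and at Day 1 pre-dose.
- Severity: "Changes in the severity of an AE should be documented" (protocol 11.4.1.2), so that the time spent at each grade can be worked out. For intermittent AEs the same paragraph asks for the onset and duration of every episode.
- Definition of an AE: SAP 17.1.1 includes "any new untoward medical occurrence or worsening of a preexisting medical condition in a clinical investigation participant". Protocol 11.4.1.1 lists "Pre-existing medical conditions judged by the Investigator to have worsened in severity or frequency or changed in character during the protocol-specified AE reporting period".

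For laboratory data, protocol 12.3.1.3 calls a graded abnormality treatment emergent if it appears after study drug starts and is at least one grade above baseline. SAP 17.1.3 plans a summary of treatment-emergent graded toxicities without repeating that definition.

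**The concern.** AEs are part of the primary endpoint, and SAP 9.2.4.1 names them as a critical dataset. The tables that show which events occurred, how severe they were and whether they were judged related are all restricted to TEAEs. If an AE is open when the infusion starts and then rises in grade, that rise is information about tolerability after dosing, yet a test on start time does not see it.

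The case can arise in this trial. As an illustration, discomfort at the cannula site could begin at insertion and intensify during the infusion. Protocol 4.5.3 lists pain and phlebitis among the infusion risks and gives an infusate pH of about 4.0 to 5.0. Local tolerability of the IV route is also a new question, because the completed human study used IM injection.

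The omission is out of step with the rest of the plan. A laboratory value in the same situation counts. SAP 17.1.1 is otherwise cautious with AEs: missing severity is taken as severe, missing relationship as related, and missing start times as post-dose.

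**Working it through.** The plan states no figure on this point, so there is none to reproduce. The check traces cases through the rule and then sizes one subject.

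**Which rule governs.** SAP 3.0 says the SAP supersedes the protocol's statistical considerations. Within the SAP, 9.2.3 is the explicit derivation, so it is the test applied below.

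**Four kinds of post-dose worsening under SAP 9.2.3.**

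1. A medical-history condition worsens after the infusion. Both documents make the worsening an AE in its own right. Its start is post-dose, so it is a TEAE.
2. An intermittent AE recurs after the infusion. Each episode has a documented onset. If episodes are entered as separate records, the post-dose one is a TEAE.
3. A continuous AE recorded after consent is open at infusion and worsens, and the increase is entered as a new dated record. The new start is post-dose, so it is a TEAE.
4. The same AE is kept as one record with its original start. That start precedes the first dose, so it is not a TEAE.

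Only case 4 is lost. The documents do not say whether case 3 or case 4 applies.

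**Where a case 4 event appears.**

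- Table 14.3.1.1: in the count of subjects with any AE, but not in the TEAE count. As described, this table gives no term, grade or relationship.
- Tables 14.3.1.2, 14.3.1.3 and 14.3.1.4: absent.
- Listing 16.2.7.1: present, because all AEs are listed whether treatment emergent or not.

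**Weight of one subject.** Group sizes come from protocol 7.2: 6 galidesivir and 2 placebo per cohort, four cohorts, placebo pooled. That gives 6 × 4 = 24 galidesivir and 2 × 4 = 8 placebo. For a subject not already counted in the row, the change is 1/n:

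- galidesivir cohort: 1/6 = 16.7 percentage points
- pooled placebo: 1/8 = 12.5 points
- all galidesivir: 1/24 = 4.2 points

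If 0 to 2 such subjects fell in one group (an assumption), the range would be 0 to 2/6 = 33.3 points in a galidesivir cohort, or 0 to 2/8 = 25.0 points in pooled placebo.

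**How many subjects.** The expected number is 32 × P(AE open at dosing) × P(it worsens) × P(kept as one record). The documents give none of the three probabilities. Assuming 5% to 10% for the first gives 32 × 0.05 = 1.6 to 32 × 0.10 = 3.2 subjects with an open AE. These are candidates only. The other two factors are at most 1 and unknown, so under that assumption the expected number lies between 0 and 3.2.

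**Direction.** Compared with a definition that includes worsening, the rule can only lower the TEAE count in each group. Placebo subjects are affected too, so the direction of any effect on the difference between galidesivir and placebo is not fixed.

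**The case against.** A reader might infer that any pre-dose AE that worsens is simply not counted in the primary safety tables. The documents do not support that, for three reasons.

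- Worsening of a pre-existing condition is itself an AE in both documents and would normally have a post-dose onset, so much worsening already qualifies.
- Whether a severity change stays in one record or opens a new one is not stated, and the eCRF is not among the documents. Working out time at each grade needs dates for each grade, which fits split records. On the other hand, protocol 11.4.1.2 describes one event with several intensities and asks for a separate onset only for intermittent AEs, which fits a single record. The text leans that way but does not settle it.
- A case 4 event is still in the overall AE count and the listing. With 32 subjects, the listing can be read in full.

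It can also be said that the wording in protocol 12.3.1.3 and SAP 17.1.1 speaks of events occurring after dosing, which could be read to include worsening. That is fair, but SAP 9.2.3 is the operative derivation and leaves no such room.

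The difference from the laboratory rule is not a contradiction. Laboratory values have a measured baseline grade and AEs do not, and measured worsening is captured separately in the laboratory shift tables, vital-sign changes and QTcF change categories. The difference does show that the plan regards worsening from baseline as treatment emergent where it considered the question.

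Safety decisions during the trial do not rest on the TEAE tables alone. The Dose Escalation Committee receives a listing of AEs with severity (protocol 11.5.2), and the study halting rule on Grade 3 AEs (protocol 7.6.3.2) is not limited to TEAEs.

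Finally, subjects are screened healthy volunteers whose eligibility is rechecked on Day -1, so few should have an AE open at dosing.

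**Conclusion.** There is a real but narrow gap. An AE recorded after consent, ongoing at infusion, kept as a single record and worsening after the dose would be left out of Tables 14.3.1.2 to 14.3.1.4. Without a written rule, its classification depends on data-entry practice that neither document describes.

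The number of affected subjects cannot be derived from the documents and may be zero. The 16.7-point and 12.5-point figures are the weight of one subject, and apply only if that subject has no other TEAE in the same row. They are not estimates of likely bias. The 5% to 10% used above is an assumption about AEs open at dosing, not about AEs that worsen.

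No planned analysis fails and no design figure changes. The point merits correction because the omission understates post-dose worsening in tables supporting the primary endpoint, and a short clause removes it.

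**What to change.** In SAP 9.2.3 and 17.1.1, and for consistency in protocol 12.3.1.3, define a TEAE as an AE that starts on or after first dose, or that started earlier and increases in severity on or after first dose. Report the second kind at its worst post-dose severity.

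To support this, state that a post-dose severity increase is entered on the eCRF with its own date and time. An alternative is to state that such an increase opens a new AE record with its own start date and time. The existing test in SAP 9.2.3 would then classify it correctly without rewording.

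The SAP change is one clause and leaves the design and the list of outputs as they are. The cost lies in the data: dated severity changes must be in the analysis database, not only in source. The protocol requires them to be documented but does not say they reach the eCRF. If they are already separate dated records, only the clarification is needed. If they are held only in source, they would have to be entered for the few AEs open at dosing.
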